**Consent:**

Once a patient has been identified as a confirmed positive case of COVID-19, they will be called for e-consent. A link to REDCap will be sent and the patient will be asked to access it via their personal device to minimize contact between patients and research staff. An outline of the study will be presented and the participant will be free to ask questions and carefully consider whether or not to participate. They will receive a copy of their signed consent form via email.

## 6. STUDY DESIGN AND PROCEDURES

1. Patients will be screened via the electronic medical system, and/or noted and communicated to the study team by physicians in the units.
2. Patient will be called for e-consent.
3. Patients of childbearing potential will receive a pregnancy test
4. Enrolled patients will be randomized to intervention or control with random permuted blocks of 2-4 via sealed envelope or secured electronic randomization tool that will be selected after consent. Patients or treating clinicians will not be notified of treatment assignment.
5. Amniotic fluid will be procured by the Cell Therapy and Regenerative Medicine group here at the University of Utah. Product will be delivered, either frozen or thawed, by this group to the relevant hospital unit/floor.
6. After consent, but prior to initial intervention, the following measurements will be collected:
  - a. Demographics (age, sex, height, weight, race/ethnicity, study hospital admit date and time)
  - b. Medical history
  - c. Concomitant medications
  - d. Confirmation of negative pregnancy test, if applicable
  - e. Date of symptom onset
  - f. Date of confirmed SARS-CoV-2 positivity by RT-PCR
  - g. Vital signs (heart rate, blood pressure, oxygen saturation, respiratory rate, temperature)
    - a) Patients must have a blood pressure of <160/96 mmHg prior to receiving study IP
    - b) Patients must have a pulse of <110 beats per minute prior to receiving study IP
  - h. Glasgow Coma Scale
    - a) Patient must have a GCS score of  $\geq 14$  prior to consent
  - i. Respiratory support modality and settings
  - j. Complete blood count with auto differential
  - k. Complete metabolic panel
  - l. Blood glucose (for patients with diabetes)
  - m. Inflammatory biomarkers (interleukin-6, c-reactive protein, d-dimer, lactate dehydrogenase)
  - n. Results of chest x-ray and/or chest CT, if available.
7. Patients will receive either 10ml IV hAF or 10ml normal saline (control) each day for 5 consecutive days. hAF and saline with similar lot numbers will be prepared in order to maintain blinding between both clinicians and patients.
8. For 3 hours following IP administration, patients will be placed on continuous monitoring (e.g., pulse oximetry, blood pressure) and monitored for infusion reactions.
9. Assessments on Days 1-5 will include:
  - a. Intervention or control date and time

- b. Vital signs (heart rate, blood pressure, oxygen saturation, respiratory rate, temperature)
  - a) Patient must have a blood pressure of <160/96 mmHg prior to receiving study IP
  - b) Patient must have a pulse of <110 beats per minute prior to receiving study IP
    - i. In the event that a patient does not meet blood pressure and/or pulse criteria for IP administration, these vital signs will be rechecked every hour until they have returned to the necessary range.
- c. Glasgow Coma Scale
- d. Respiratory support modality and settings
- e. Blood glucose (for patients with diabetes)
- f. Results of chest x-ray and/or chest CT, if available.
- g. Concomitant medications

10. Day 6 (post-intervention) assessment will include:

- a. Vital signs (heart rate, blood pressure, oxygen saturation, respiratory rate, temperature)
- b. Glasgow Coma Scale
- c. Respiratory support modality and settings
- d. Complete blood count with auto differential\*
- e. Complete metabolic panel\*
- f. Blood glucose (for patients with diabetes)
- g. Inflammatory biomarkers (interleukin-6, c-reactive protein, d-dimer, lactate dehydrogenase)\*
- h. Results of chest x-ray and/or chest CT, if available
- i. Concomitant medications

\*Patients who have been discharged from the hospital prior to Day 6 will be asked to return to the hospital or an outpatient clinic for Day 6 lab work.

11. At ICU discharge (if applicable) and hospital discharge, the following will be gathered:

- a. Intervention or control date and time
- b. Vital signs (heart rate, blood pressure, oxygen saturation, respiratory rate, temperature)
- c. Glasgow Coma Scale
- d. Respiratory support modality and settings
- e. Blood glucose (for patients with diabetes)
- f. Results of chest x-ray and/or chest CT, if available.

12. The following data will be collected following hospital discharge:

- a. Last available results of chest x-ray(s) and/or chest CT(s), if available.
- b. ICU admit and discharge dates and times (if applicable)
- c. Hospital floor admit and discharge dates and times
- d. Dates and times of intubation and extubation (if applicable)
- e. Tracheostomy (if applicable)
- f. ECMO status (and settings, if applicable)
- g. Major adverse cardiac events

- h. Discharge date and time
- i. Discharge location
- j. Concomitant medications
  - a) Including but not limited to current COVID-19 therapies not approved by the FDA, and non-pharmaceutical therapies
- k. Date and time of death (if applicable)

13. Safety assessments will be performed at 30, 60, 90 and 180 days (+/- 7 days) post-discharge

- a. Safety assessments will include a defined script inquiring about any new or remaining symptoms (e.g., shortness of breath), sleep quality, if the patient feels they are back to baseline and if they have any positive or negative feedback regarding the IP. Open-ended questions regarding any additional concerns the participant may have as well as a specific question regarding any health events or hospitalizations since the last assessment will also be asked.
- b. These assessments will be performed remotely via telephone by study staff. If the assessment is positive (i.e., if the patient reports AEs that are determined to be related to study drug), a clinician will arrange a telemedicine visit to follow up.

14. At 1, 3, 6, and 12 months post-discharge, patients will be emailed a REDCap survey link in order to complete several surveys: PROMIS measures including Dyspnea Severity, Physical Function, Sleep Disturbance, Anxiety, and Depression, as well as the PTSD Checklist (PCL).

- a. If the patient is still hospitalized at any of these time points, respiratory settings and details of physical therapy progress will be gathered from the chart instead.
- b. Window: 1 month +/- 7 days, 3/6/12 months +/- 14 days

15. If a patient is discharged prior to receiving the 5-days of IP administration the patient will still be followed for the duration of the study

Primary Outcome:

1. C-reactive protein levels as assessed prior to and following intervention.

Secondary Outcomes:

1. Death within 30 days
2. ICU-free days at 30 days
3. Hospital length of stay
4. Need for invasive mechanical ventilation
5. Biomarker levels (interleukin-6, d-dimer, lactate dehydrogenase)
6. Need for ECMO
7. Major adverse cardiac events
8. Patient-reported functional status

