**1. SYNOPSIS**

Title	A Phase I/II Randomized, Double-Blinded, Placebo-Controlled Clinical Trial to Determine Safety and Feasibility of Using an Acellular Sterile Filtered Amniotic Fluid as a Treatment for COVID-19 Patients.
Short Title	hAF for the Treatment of COVID-19
IRB Number	IRB: 00132922
IND	IND # 23369
Phase	Phase I/II
Design	This is a prospective double-blinded, randomized controlled study to determine the safety and feasibility of using processed sterile filtered amniotic fluid (hAF) to treat and reduce inflammation in COVID-19 patients.
Study Duration	1 year
Study Center(s)	University of Utah
Objectives	
Primary Objectives:
 

• To determine the safety of using processed human amniotic fluid (hAF) intravenously (IV) to treat patients with COVID-19.

• To determine efficacy of hAF vs. placebo to reduce inflammation in COVID-19 patients.

• To determine clinical outcomes in patients treated with hAF vs. placebo.

Number of Subjects	60 patients (30 per treatment arm)
Eligibility Criteria	
Inclusion:
 

1. Age <math>\geq 18</math>

2. SARS-CoV-2 positivity by RT-PCR test, obtained within 14 days of enrollment

3. Hospitalized

4. COVID-19 symptomatic (cough, fevers, shortness of breath, and/or sputum production)

5. Has a room air pulse oximetry of <math>\leq 94\%</math> and requires supplemental oxygen therapy

6. Patients of child bearing potential who agree to use acceptable methods

	
of contraception for 90 days after last administration of study IP
 
7. Patients who are receiving standard of care therapies for COVID-19 that are not FDA approved are eligible for this study
 
8. Patients must be able to consent to the study (e.g. Glasgow Coma Score of <math>\geq 14</math>)
 
9. Patients are required to have controlled blood pressure of <math>< 160/96</math> and have a pulse of <math>< 110</math> at the time of study drug administration.

--	--

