## **8. STATISTICAL CONSIDERATIONS**

### **Statistical Methods**

This is a trial with patients randomized to two groups: (1) treatment group with hAF administered intravenously (n=30), (2) control group with intravenous administration of a saline control (n=30). Both groups will receive standard of care in addition to these treatments.

Descriptive statistics, including mean (SD) and median (interquartile range), will be used to assess patient characteristics, and clinical and biomarker outcomes. Comparisons will be made stratified on ICU vs floor status at enrollment for variables. Categorical characteristics will be compared using chi-square test or Fisher exact test. Continuous characteristics will be compared using independent samples t-test or Wilcoxon-Mann-Whitney test. 95% Confidence intervals and *p*-values will be reported from all comparisons. Statistical analyses will be conducted in R and STATA, significance will be assessed at the 0.05 level and all tests will be two-tailed.

Safety will be assessed by descriptive reporting of the incidence proportion of study-related safety adverse events in each study group, with one-sided 95%

binomial exact confidence intervals. No statistical hypothesis test is planned to assess safety, which is consistent even with large Phase III trials. The table below displays the number of patients, out of 30, experiencing no adverse event and the corresponding lower-bound of the 95% exact confidence interval.

Number of Patients with no Related Adverse Events	Number of Patients Experiencing a Related Adverse Event	Lower-bound of the 95% Exact Binomial Confidence Interval for Safety
30	0	90%
29	1	85%
28	2	80%
27	3	76%

If there are 30 patients in the hAF group and if all patients in the hAF group complete the study without experiencing an adverse event we will be able to state with 95% confidence that the safety of hAF is at least 90%.

Exploratory outcomes for safety include, but are not limited to, the following:

- Whether the patient experienced any post-randomization AEs while on study (regardless of relatedness to study participation)
- Whether the patient experienced any post-randomization serious AEs while on study
- Whether the patient experienced any post-randomization unexpected AEs while on study.

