## **Sample Size Justification**

A sample size of  $n = 30$  patients per group (total  $n = 60$ ) is expected, though this may differ slightly because of the randomization procedure. If we are unable to enroll 60 patients due to lack of cases, we will expand the study to other hospitals. The IRB application shows an enrollment goal of 65, which is to allow space to continue enrolling and meet the goal of an  $n = 60$  in the event of participant withdrawal.

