## 10. PROTECTION OF HUMAN SUBJECTS

### Institutional Review Board Approval

Each clinical center must obtain approval from their respective IRBs prior to participating in the study. CellReGen will track IRB approval status at all participating centers and will not permit subject enrollment without documentation of initial IRB approval and maintenance of that approval throughout subsequent years of the project.

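### Randomisation names no stratification factor, although the analysis is to be stratified on ICU versus floor at enrolment; running the blocks within ICU and floor is a nearly free improvement

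*Combined protocol and SAP*

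**What the plan says.** Section 6, Study Design and Procedures, item 4: "Enrolled patients will be randomized to intervention or control with random permuted blocks of 2-4 via sealed envelope or secured electronic randomization tool". No stratification factor is given there or anywhere else in the document.

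Section 8, Statistical Methods: "Comparisons will be made stratified on ICU vs floor status at enrollment for variables". The tests listed are chi-square or Fisher for categorical variables and t-test or Wilcoxon-Mann-Whitney for continuous ones. No stratified estimator, covariate or site term is named.

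The Synopsis gives the size as "60 patients (30 per treatment arm") and lists one centre. The Sample Size Justification adds a contingency: "If we are unable to enroll 60 patients due to lack of cases, we will expand the study to other hospitals". It also accepts that group sizes may depart slightly from 30 because of the randomisation procedure. Section 10 is worded for several centres: "Each clinical center must obtain approval from their respective IRBs prior to participating in the study".

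**The concern.** The sponsor chose ICU versus floor at enrolment as the factor on which to stratify comparisons, so the plan itself treats it as prognostic. Because it is known before allocation, it could be used in the randomisation at almost no cost. Permuted blocks without strata balance only the arm totals, not the number of ICU patients in each arm.

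Two things are at stake with 30 per arm. The comparison inside the ICU stratum may rest on an uneven split of few patients. And any comparison not adjusted for ICU status carries avoidable noise and invites doubt if the arms visibly differ at baseline. ICU-free days at 30 days is an obvious case, since it depends directly on where the patient starts. If hospitals are added, a smaller and conditional version of the same question arises for site.

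**Working it through.** The plan gives no figure on covariate balance to reproduce, and no ICU share.

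**Inputs.** From the documents: 60 patients, 30 per arm, blocks of 2-4. Assumed: block sizes 2 and 4 with equal chance; m ICU patients among 60, with m = 6, 12, 18, 24 or 30 (10% to 50%).

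**Chance imbalance as the plan stands.** With m fixed, the number K of ICU patients in the hAF arm is approximately hypergeometric (60 patients, m in ICU, 30 drawn). The gap between arms is |2K - m|. For m = 12, a gap of 4 or more means K ≤ 4 or K ≥ 8, which has probability 0.333.

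| ICU patients of 60 | P(gap ≥ 4) | P(gap ≥ 6) |
|---|---|---|
| 6 | 19.5% | 2.4% |
| 12 | 33.3% | 10.4% |
| 18 | 39.9% | 15.8% |
| 24 | 43.0% | 18.7% |
| 30 | 43.9% | 19.6% |

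Simulating the blocks themselves gave the same values to within about one percentage point.

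**Cost under a stratified comparison.** Assume equal variance in both strata. The information is the sum over strata of n1·n0/(n1 + n0), and the standard error is proportional to 1/√information. Perfect balance gives 15.
- m = 12, gap 4: ICU 8:4 gives 32/12 = 2.667; floor 22:26 gives 572/48 = 11.917; total 14.583. SE ratio √(15/14.583) = 1.014.
- m = 12, gap 6: 27/12 + 567/48 = 2.250 + 11.813 = 14.063. SE ratio 1.033.
- m = 30, gap 4: 221/30 + 221/30 = 14.733. SE ratio 1.009.
- m = 6, gap 4: 5/6 + 725/54 = 0.833 + 13.426 = 14.259. SE ratio 1.026.

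Averaged over the hypergeometric distribution, the loss is about 0.9%.

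**Cost inside the ICU stratum.** The SE is proportional to √(1/n1 + 1/n0).
- 12 ICU patients: 8:4 against 6:6 gives √(0.375/0.333) = 1.06; 9:3 gives √(0.444/0.333) = 1.15.
- 6 ICU patients: 5:1 against 3:3 gives √(1.2/0.667) = 1.34; at 6:0 there is no comparison.

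**Cost if ICU status is ignored.** Suppose ICU and floor patients differ by 0.5 to 1 SD on the outcome (assumed). A gap of 4 shifts the mean difference by 4/30 × (0.5 to 1) = 0.07 to 0.13 SD. The SE is √(2/30) = 0.258 SD, so the shift is 0.26 to 0.52 SE. A gap of 6 gives 0.39 to 0.77 SE.

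**With blocks run within ICU and floor.** In simulation over all five values of m, the ICU gap never exceeded 2. Arm totals never differed by more than 4, and a difference of 4 occurred in under 1% of runs.

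**Added hospitals.** Assume a late-joining hospital contributes 20 of the 60 patients and shares the existing sequence. If it supplies all late enrolment, its arms differ by 4 or more in about 0.6% of runs and never by 6. If it supplies 75% of late enrolment, a gap of 6 or more occurs in about 4%; if half, about 12%. If instead blocks run within ICU/floor by hospital (30% ICU, equal-sized hospitals, both assumed), a difference of 10 points or more in ICU share occurs in 0.1% of runs with two hospitals, 1% with three and 4% with five.

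**The case against.** The strongest reply is that counting patients overstates the harm. Randomisation without strata is valid. Chance imbalance is already part of ordinary sampling error, so it neither biases the comparison in expectation nor inflates type I error. The planned ICU/floor stratification removes most of what remains, at an average cost near 1%. The exclusions (invasive and non-invasive ventilation, the highest oxygen needs, impending respiratory failure) also narrow the severity range and may leave few ICU patients. All of this stands. A small ICU stratum lowers the chance of a large gap but makes the within-ICU split more fragile when one occurs.

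Three stronger readings are tempting and are not supported.
- A reader might infer that the protocol prescribes a single unstratified sequence. It says neither; it only names no factor.
- A reader might infer that an imbalance would produce a false hAF effect. The shifts above stay below one standard error under the assumed severity differences, and the error rate is unaffected.
- A reader might infer that a late-joining hospital would fall mostly in one arm, or that envelopes could not cope. Small blocks largely prevent the first where the hospital dominates late enrolment, and a separate envelope set at each hospital would itself be a site-specific list. Expansion is in any case conditional on a lack of cases.

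**Conclusion.** The mismatch is real: the analysis uses ICU versus floor and the randomisation, as described, does not. Its consequence is modest. An ICU gap of 4 or more has a chance of about 20% to 44%, and of 6 or more about 2% to 20%, over assumed ICU shares of 10% to 50%. Validity is intact. What suffers is the within-ICU comparison and the precision and credibility of any unadjusted result. The stratified comparison offsets most of the loss only if it is actually carried out, and no estimator for it is named.

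The site question is secondary and depends on an expansion that may not happen. The sizes rest on the assumed ICU share, equal use of block sizes 2 and 4, equal variances and, for site, assumed hospital sizes. This is an optional improvement, worth making because balance cannot be restored after enrolment.

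**What to change.** Amend item 4 so that the permuted blocks run separately within ICU and within floor, by status at enrolment, and keep the same factor in the analysis.

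If hospitals are added, keep ICU/floor as the stratum and state in advance whether each hospital has its own lists or whether site is adjusted for in the analysis. With many small hospitals the second is preferable, because crossing site with ICU status leaves blocks unfilled.

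The cost is a second list and one amended sentence, submitted as a protocol amendment, with no extra patients or data. The downside is that arm totals may differ by up to 4 instead of 2, a departure of the kind the Sample Size Justification already tolerates.

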### Secondary Endpoint:

- Other endpoints include mean days of supplemental oxygen, mean days of mechanical ventilation, mean ICU and hospital length of stay, and patient-reported functional status.
- Survival at days 7, 14, 60, 90 days post randomization.

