**Time Period for Adverse Events**

For purposes of this study, events that occur following randomization through the Day 180 will be reported as adverse events. Serious adverse events, unexpected medically attended events, and new onset chronic illnesses will be recorded from randomization through Day 180. Specifically, events that occur following informed consent to participate in the study, but prior to actual randomization are not adverse events. These should be recorded as baseline conditions.

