#### Potential Benefits

We are in an unprecedented global crisis with the spread of the COVID-19 pandemic. The data showing that babies born to COVID-19 infected mothers do not have the virus, and neither is it found in breastmilk or amniotic fluid, suggests a possible treatment for this rampant infection. While it would not cure the virus itself, it has the potential to decrease inflammation and fibrosis, thus possibly making critical respiratory treatments less necessary. Considering the possible shortage of ventilators, this could be greatly beneficial to everyone currently battling this pandemic.

It cannot be guaranteed that patients themselves would benefit, as this is an experimental treatment. However, if our hypothesis is correct, it is possible that COVID-19 infected patients would see a reduction of respiratory inflammation and fibrosis. This could result in more effective treatment, shorter hospitalization, and less use of critical resources.

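### Does the rule for patients still in hospital mean that the PROMIS and PTSD surveys need a different time origin?

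*Combined protocol and SAP*

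**What the plan says.** Section 6, item 14 schedules the PROMIS measures and the PTSD Checklist: "At 1, 3, 6, and 12 months post-discharge, patients will be emailed a REDCap survey link". Item 14b adds tolerances: "Window: 1 month +/- 7 days, 3/6/12 months +/- 14 days". Item 14a provides a substitute, chart data on respiratory settings and physical therapy, for use as follows: "If the patient is still hospitalized at any of these time points".

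The item just before it, item 13, uses the same origin for the telephone calls: "Safety assessments will be performed at 30, 60, 90 and 180 days (+/- 7 days) post-discharge".

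Two other schedules count from randomization. Section 3 lists "Survival at days 7, 14, 60, 90 days post randomization", and the adverse event period in section 7 reads "events that occur following randomization through the Day 180 will be reported as adverse events".

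Patient-reported functional status is secondary outcome 8 in section 6. Neither that list nor section 3 gives it an instrument, a time point or an origin. Hospital length of stay is itself a secondary outcome. Section 10, under Potential Benefits, says of hAF: "This could result in more effective treatment, shorter hospitalization, and less use of critical resources". The same passage says that benefit to patients cannot be guaranteed.

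**The concern.** A patient cannot still be in the index stay at a time counted from the end of that stay. Read literally, item 14a has nothing to do until a patient is readmitted, and the word *still* fits readmission badly. That suggests item 14a was written with an earlier origin in mind, perhaps randomization, enrollment or admission, so that the two items disagree about when the surveys fall due.

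The second worry is statistical. With a discharge origin, the time from randomization to survey includes the length of stay, which treatment may change. If hAF shortened the stay, treated patients would answer the 1-month survey earlier after randomization than placebo patients. Part of any score difference could then reflect timing rather than treatment. The comparisons in section 8 (t-test or Wilcoxon-Mann-Whitney, stratified on ICU or floor status at enrollment) do not adjust for assessment time.

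At stake is, presumably, secondary outcome 8. The CRP endpoint and the 5-day adverse event endpoint are not touched.

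**Working it through.** The plan states no figure to reproduce here; the check is date arithmetic and a comparison of passages.

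**Inputs.** Survey times and windows are from items 14 and 14b, taking the months as 30, 90, 180 and 365 days. L is the number of days from randomization to discharge. The documents do not give L, so every value below is an assumption.

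**Step 1: timing as written.** Day of the 1-month survey since randomization = L + 30, with window L + 23 to L + 37.

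| L (assumed) | Target day | Window |
|---|---|---|
| 3 | 33 | 26–40 |
| 7 | 37 | 30–44 |
| 14 | 44 | 37–51 |
| 21 | 51 | 44–58 |
| 45 | 75 | 68–82 |

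The target moves one for one with L. Two patients' windows stop overlapping once their stays differ by more than 7 + 7 = 14 days.

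**Step 2: a difference between arms.** Let the mean stay be 10 days on placebo and d days shorter on hAF. The shift as a share of elapsed time is d / (10 + survey day).

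| d | 1 month (40) | 3 months (100) | 6 months (190) | 12 months (375) |
|---|---|---|---|---|
| 2 | 5.0% | 2.0% | 1.1% | 0.5% |
| 5 | 12.5% | 5.0% | 2.6% | 1.3% |
| 10 | 25.0% | 10.0% | 5.3% | 2.7% |

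The last row is a limit: 10 − 10 = 0 puts hAF discharge on the day of randomization. With a 20-day placebo stay the 1-month shares are 2/50 = 4%, 5/50 = 10% and 10/50 = 20%. These are shares of time, not biases in a score. Converting them would need a recovery slope, which the documents do not give.

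**Step 3: the alternative clock.** Counted from randomization, the 1-month survey falls on day 30 for everyone (window 23 to 37), and item 14a can operate when L exceeds 30. Time since discharge is then 30 − L: 20 days if L = 10 and 10 days if L = 20. A 5-day difference in stay (L = 10 against L = 5) gives 20 against 25 days since discharge. On the discharge clock the same pair gives 40 against 35 days since randomization. The 5 days move from one time scale to the other.

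Two further costs follow.
- Patients in hospital beyond day 30 + 7 = 37 supply chart data that cannot be scored on the questionnaires. If 0 to 3 of 30 per arm stay that long (assumption), 0% to 3/30 = 10% of an arm's 1-month scores are lost, possibly unequally by arm.
- The surveys no longer line up with the item 13 calls. The 1-month survey on day 30 comes L days before the 30-day call, which falls on day 40 if L = 10 and day 50 if L = 20.

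**Step 4: which origin the text supports.** Item 14 names discharge. Item 13 names discharge too, and its 30-, 90- and 180-day calls match the 1-, 3- and 6-month surveys. The passages that count from randomization govern survival and adverse events, not surveys. Item 14a suggests an earlier origin but names none.

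**The case for a change.** The best case for a change is that items 14 and 14a cannot both work during the index stay, and no other passage says in terms which clock governs the surveys. A coordinator who takes item 14a seriously could schedule a long-stay patient differently from one who follows item 14. Length of stay is an outcome that hAF is hoped to improve. A difference between arms in survey timing is therefore foreseeable, and the ± 7-day window does not cancel it: the window allows scatter in both arms and leaves a systematic shift in place. Naming one origin would cost almost nothing.

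The wording mismatch stands, and so does the dependence of survey day on length of stay. The rest is weaker. Scheduling by randomization means overriding an explicit word in item 14 on the strength of a contingency clause that does not mention randomization. The timing shift follows from any discharge origin, and measuring recovery from the day a patient leaves hospital is a recognised choice, not an error. The bias argument needs three things the documents do not supply: an effect of hAF on stay, a recovery slope at about one month, and a stated link from these surveys to outcome 8. Rewording or deleting item 14a would tidy the text but alter no result, because under item 14 the surveys go out after discharge whether or not item 14a is there.

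**Conclusion.** No change to the plan follows. Item 14a is a clerical looseness: followed as written, the surveys are sent on the discharge clock and the clause stays idle during the index stay. At most it would cover a readmission, which is foreseeable, since item 13a asks about hospitalizations since the last contact.

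The choice of discharge over randomization is a fair trade-off. With an assumed 10-day placebo stay and differences of 2 to 5 days, the timing shift at 1 month is 5% to 12.5% of elapsed time. Both differences are smaller than the 7-day tolerance, and by 12 months they are 0.5% to 1.3%. Counting from randomization would give a comparable imbalance in time since discharge, lose up to an assumed 10% of an arm's 1-month scores, and break the alignment with the item 13 calls.

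An analyst who wants to examine timing can do so without touching the schedule. Dosing date and time (item 9a) and discharge date and time (item 12h) are already collected, so days since first dose at each survey can be derived, given the survey completion date. The conclusion rests on assumed stays and on taking discharge in item 14 to mean discharge from hospital. It would need another look only if the sponsor said that an earlier origin was intended.

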**Exclusion:**

1. Patients on invasive mechanical ventilation (e.g., endotracheal intubation)
2. Chronic home oxygen utilization
3. Clinically significant home use of immunosuppressive medications, including more than 20mg of steroid (e.g., prednisone) per day, monoclonal antibodies, or chemotherapy medications. Patients who are not chronically immune suppressed are eligible for participation. Patients who are prescribed steroids, including dexamethasone, for the purpose of treating COVID-19 prior to the patient's study hospital admission will not be excluded.
4. Women who are pregnant, breastfeeding or become pregnant during the study
5. Patients on non-invasive positive pressure ventilation
6. Patients on  $>12$  liters per minute via non-rebreather (NRB) or  $>80\%$  oxygen via high flow nasal cannula
7. Patients who in the opinion of the Investigator has impending respiratory failure, defined as requiring rapidly escalating oxygen supplementation
8. Patients with a hemoglobin  $< 9$  mg/dL
9. Patients diagnosed with stage 4 or 5 chronic kidney disease (CKD)
10. Patients with diagnosed with NYHA class 3 or 4 congestive heart failure (CHF)
11. Patients with a left ventricular assist device (LVAD)
12. Patients with thromboembolic phenomena
13. Patients with Type 2 and above heart block
14. Patients with established positive bacterial blood cultures prior to enrollment
15. Patients with ongoing pericardial effusion, or ascites
16. Patients with clinically significant arrhythmia
17. Patients with liver function tests (ALT or AST)  $> 3X$  normal
18. Patients with untreated HIV infection
19. Patients diagnosed with end-stage organ disease

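### Analysed as written, the ventilation outcome puts patients who die without intubation in the same category as patients who recover, which favours hAF if such deaths are more frequent on hAF

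*Combined protocol and SAP*

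**What the plan says.** The secondary outcome lists in Section 1 (Statistical Methodology) and Section 6 include "Need for invasive mechanical ventilation" without a definition, a time window or a rule for death. Death is a separate outcome: "Death within 30 days" in the same lists, and "Survival at days 7, 14, 60, 90 days post randomization" in Section 3.

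Section 8 (Statistical Methods) states "Categorical characteristics will be compared using chi-square test or Fisher exact test". It promises confidence intervals and p-values from all comparisons, and "significance will be assessed at the 0.05 level and all tests will be two-tailed". It names no composite outcome and no competing-risk method.

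Section 5 excludes patients already on invasive ventilation, so intubation can only happen after entry. Item 12 of Section 6 collects dates and times of intubation and of death. For ECMO it collects status and settings, with no date listed.

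**The concern.** A patient who dies without intubation has no intubation date. In a two-by-two table of ventilated yes or no, that patient sits with those who went home well. Nothing in the design closes this route. Patients enter hypoxic and on supplemental oxygen, and neither eligibility list mentions a decision not to intubate, although a patient with such a decision cannot have the event however badly they do.

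The comparison matters to the trial's rationale. The background (Section 4) and the potential benefits (Section 10) speak of less critical care and less need for respiratory support, so a lower ventilation rate on hAF would attract attention. It should not be possible for deaths to improve it.

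**Working it through.** **Inputs.** From the plan: 30 patients per arm, two-sided 0.05, Fisher exact test. The plan gives no expected rate of intubation or death and no power for this outcome, so there is no stated figure to reproduce. All event rates and counts below are assumptions. The tests ignore the ICU/floor stratification in Section 8.

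**1. Size of the distortion.** Let V be the number ventilated and D the number who died without ventilation. The difference (hAF minus control) in ventilation-or-death equals the difference in ventilation alone plus (D on hAF − D on control)/30. The distortion is therefore the surplus of un-intubated deaths on hAF divided by 30: 1/30 = 3.3 percentage points per patient, and zero when D is equal in the two arms.

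**2. How many patients could be affected.** 60 × mortality × share of deaths un-intubated. With 5–20% mortality and a 20–60% share, this runs from 60 × 0.05 × 0.20 = 0.6 to 60 × 0.20 × 0.60 = 7.2 patients across both arms.

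**3. Illustrative counts.** Control has 6/30 ventilated and no un-intubated deaths.

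| hAF: V + D | Ventilation alone, hAF vs control | p | Ventilation or death, hAF vs control | p |
|---|---|---|---|---|
| 3 + 3 | 10% vs 20% | 0.47 | 20% vs 20% | 1.00 |
| 0 + 6 | 0% vs 20% | 0.024 | 20% vs 20% | 1.00 |
| 2 + 6 | 7% vs 20% | 0.25 | 27% vs 20% | 0.76 |

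In the last row hAF looks better on ventilation and is worse on ventilation-or-death. Only the extreme second row reaches significance.

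**4. Chance of a falsely significant benefit.** Give both arms the same total risk R of ventilation or un-intubated death, and let s be the share of those events that are un-intubated deaths. The ventilation risk is R(1 − s). Sum the binomial probabilities of all outcomes with fewer ventilated on hAF and Fisher p < 0.05.

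| R | Ventilated hAF vs control, s = 50% vs 10% | Ratio | Chance, s = 50% vs 10% | Chance, s = 10% in both |
|---|---|---|---|---|
| 10% | 5% vs 9% | 0.56 | 1.2% | 0.4% |
| 20% | 10% vs 18% | 0.56 | 6.3% | 1.0% |
| 30% | 15% vs 27% | 0.56 | 12.7% | 1.3% |

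With equal shares the expected ratio is 1.0. With unequal shares the ratio is well away from 1, but significance remains uncommon.

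**5. Sensitivity near the significance line.** 8/30 control vs 1/30 hAF gives p = 0.026. Counting one, two or three un-intubated hAF deaths as events gives p = 0.080, 0.18 and 0.33. Adding one such death to each arm instead (9/30 vs 2/30) gives p = 0.042. The result turns on imbalance between the arms, not on the presence of such deaths.

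**The case against.** The plan nowhere states that a death without intubation counts as no event. A reader might infer a deliberate rule that treats these deaths as successes; the documents do not support that. It is the default result of a yes/no variable in a two-by-two test. Even the choice of test is partly inferred: the chi-square/Fisher sentence speaks of characteristics, and the sentence that names clinical outcomes promises descriptive statistics. The promise of p-values from all comparisons makes testing the natural reading, but it is not explicit.

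An excess of deaths on hAF would also be visible elsewhere. Thirty-day death and survival at several times are reported. Under Section 7, any death can trigger modification or stopping pending a safety investigation, and the DSMB sees actual assignments and meets after 5, 20, 40 and 60 patients. This stands in part. It makes gross harm hard to miss, but a death count by arm does not show which deaths were un-intubated, so it cannot correct the ventilation comparison.

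A marked chance imbalance is unlikely. With 10% mortality and 40% of deaths un-intubated (4% of each arm), the probability of three or more such deaths on hAF and none on control is about 3%. That stands, and it limits the concern to the estimate more than the p-value.

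Finally, ventilator use is a legitimate question in its own right, given the plan's interest in scarce resources. That also stands, and it is why ventilation should still be reported as a component.

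**Conclusion.** The gap is real and worth closing, in a limited form. Analysed as written, the ventilation outcome merges un-intubated deaths with recoveries. It is biased towards hAF if those deaths are more frequent there, by 3.3 percentage points per surplus death. The usual consequence is a misleading point estimate. A falsely significant result needs a marked imbalance, and the 1.2% to 12.7% range rests wholly on the assumed risks and shares.

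Two stronger readings are tempting. One is that the plan will produce a false benefit; the documents give no reason to expect more un-intubated deaths on hAF, and with equal frequency there is no bias. The other is that the same argument and the same composite apply to ECMO. They do not carry over: the affected group there is everyone who dies without ECMO, intubated or not; no ECMO date is listed, so a Day 30 window may not be derivable; and if ECMO is rare (the plan gives no rate), ECMO-or-death would largely repeat the 30-day death outcome.

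This is a secondary outcome in a 60-patient Phase I/II trial, and it does not affect the CRP or adverse-event endpoints.

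**What to change.** In Sections 1, 6 and 8, make the tested outcome invasive mechanical ventilation or death from any cause through Day 30 after randomization. Report three components by arm: ventilated, died without ventilation, and alive without ventilation. Keep ECMO as a descriptive count shown beside deaths without ECMO, with no separate ECMO-or-death test.

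The cost is wording only, since intubation and death dates are already collected under item 12 of Section 6. There are two small downsides: the composite shares events with the 30-day death outcome, and ventilation use alone becomes a descriptive component.
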